4.2. Exclusion Criteria

Subjects meeting any of the following criteria will be excluded from the study:

1. Has a diagnosis of pericarditis that is secondary to specific prohibited etiologies, including tuberculosis (TB); neoplastic, purulent, or radiation etiologies; post-thoracic blunt trauma (e.g., motor vehicle accident); myocarditis; or systemic autoimmune diseases with exception of Still's disease.
2. Is pregnant, breastfeeding, or planning a pregnancy or fathering a child during the study or within 3 months after the last study drug administration.
3. Has a history of immunosuppression, including positive human immunodeficiency virus (HIV) test results.
4. Is currently receiving CS at a dose of >60 mg/day prednisone (or equivalent) for adult subjects, or >0.5 mg/kg/day (or >60 mg/day, whichever is lower) prednisone (or equivalent) in pediatric subjects (≥ 12 and <18 years old).
5. Has ever received cytotoxic drugs, including cyclophosphamide, chlorambucil, nitrogen mustard, or other alkylating agents.
6. Has ever received agents that deplete B or T cells (e.g., rituximab, alemtuzumab).
7. Has received systemic immunomodulatory agents (with exception of CS) within the following time frames prior to RI baseline (first administration of study drug):
 - a. Azathioprine, mycophenolate mofetil, cyclosporine, tacrolimus, sirolimus, or mercaptopurine within 24 weeks.
 - b. TNF inhibitors, IL-6 inhibitors, or janus-activating kinase inhibitors within 12 weeks.
 - c. Canakinumab within 12 weeks. Canakinumab could not have been discontinued due to safety unless it was discontinued due to local injection site reactions.
 - d. Rilonacept within 6 weeks. Rilonacept could not have been discontinued due to lack of efficacy or due to safety.
 - e. Methotrexate within 2 weeks.
 - f. Anakinra within 5 days. Anakinra could not have been discontinued due to lack of efficacy or due to safety unless it was discontinued due to local injection site reactions.
8. Has a history of myeloproliferative disorder.
9. Has a history of demyelinating disease or symptoms suggestive of multiple sclerosis.
10. Meets the following TB criteria:
 - a. History of active TB prior to screening OR
 - b. History of latent TB that was not adequately treated prior to screening OR
 - c. Signs or symptoms suggestive of active TB (e.g., new cough of >14 days in duration or a change in chronic cough, persistent fever, unintentional weight loss, or night sweats) upon review of medical history and/or physical examination at screening OR

- d. Recent close contact with a person with active TB OR
 - e. Positive or indeterminate Interferon Gamma Release Assay (IGRA) test results or results from another positive TB test at screening based on acceptable clinical practice for the country in which the subject is enrolling.
11. Has chest x-ray (posterior-anterior view) at screening (or history of results within 12 weeks before receiving first administration of study drug), with evidence of malignancy or abnormality consistent with prior or active TB infection.
 12. Has received immunization with a live (attenuated) vaccine within 12 weeks before screening or is expected to receive live (attenuated) vaccine during the study or within 12 weeks after the last study drug administration.
 13. Has a history of positive or intermediate results for hepatitis B surface antigen, hepatitis B core antibody, or hepatitis C virus antibody at screening.
 14. Has an estimated glomerular filtration rate (eGFR) <30 ml/min.
 15. Has a history of malignancy of any organ system within the past 5 years before screening (other than a successfully treated non-metastatic cutaneous squamous cell carcinoma or basal cell carcinoma and/or localized carcinoma in situ of the cervix).
 16. Has a known or suspected current active infection or a history of chronic or recurrent infectious disease, including, but not limited to, chronic renal infection, chronic chest infection, sinusitis, recurrent urinary tract infection, or an open, draining infected skin wound.
 17. Has had a serious infection, has been admitted to the hospital for an infection, has been treated with oral antibiotics for a documented infection within 2 weeks of RI baseline (first administration of study drug), or has been treated with IV antibiotics for an infection within 8 weeks of RI baseline.
 18. Has had an organ transplant.
 19. Has screening laboratory test results meeting any of the following criteria:
 - Hemoglobin level <10.0 g/dL
 - WBC count < $3.0 \times 10^3/\mu\text{L}$
 - Neutrophil count < $1.5 \times 10^3/\mu\text{L}$
 - Platelet count < $100 \times 10^3/\mu\text{L}$
 - Total bilirubin level > $1.5 \times$ the upper limit of normal (ULN) unless the test results are consistent with those for Gilbert's syndrome
 - Aspartate aminotransferase (AST) or alanine aminotransferase (ALT) values > $2 \times$ ULN
 20. In the Investigator's opinion, has a history of alcoholism or drug/chemical abuse within 2 years before screening.
 21. Has a known hypersensitivity to ARCALYST® (rilonacept) or to any of its excipients.

22. Has received an investigational drug during the 30 days (or 5 half-lives, whichever is longer) before screening or is planning to receive an investigational drug (other than that administered during this study) or use an investigational device at any time during the study.
23. In the Investigator's opinion, has any other medical condition that could adversely affect the subject's participation or interfere with study evaluations. This includes significant concomitant illnesses such as, but not limited to, cardiac, renal, neurological, endocrinological, metabolic, pulmonary, GI, or psychiatric diseases.
24. In the opinion of the Investigator, is not likely to be compliant with the study protocol.
25. In the opinion of the Investigator, should not participate in this study.

4.3. Subject Completion, Withdrawal from Study, and Study Drug Discontinuation

4.3.1. Completion

A subject will be considered to have completed the study if she/he has completed the RW period and has completed assessments at the EORW visit. At the EORW visit all subjects who are still receiving study treatment (blinded therapy or open-label bailout) will be offered an opportunity to receive up to an additional 24 months of open-label rilonacept treatment based on their clinical status and at the discretion of the investigator, and after signing the LTE informed consent.

Additionally, after the randomized withdrawal period has been closed when at least 22 confirmed recurrent pericarditis events have been accrued, subjects who have not yet completed the full 12 weeks of RI period at that time will be allowed to continue tapering of concomitant meds in the RI period; those subjects who achieved clinical response by Week 12 will be given the option to receive open-label rilonacept in the LTE without having to proceed through the RW period.

Any subject who in the opinion of the Investigator should not continue open-label rilonacept in LTE will be withdrawn from the study.

Subjects who elect not to enter the LTE will be followed for 6 weeks (safety follow up) after receiving the last study drug administration.

4.3.2. Reasons for Discontinuation of Study Drug and Study Withdrawal

Subjects have the right to stop taking study drug before the end of the study or to withdraw their consent for further participation in the study (i.e., precluding continued data collection). A subject also may be asked to stop study drug at the investigator's discretion. In the event that a subject permanently discontinues study drug but does not withdraw the informed consent, the investigator should continue to follow up with the subject by telephone contact (TC) visits, in the clinic, or by other means through the EORW visit if the subject discontinues in RI, RW, or LTE unless consent is withdrawn.

The reasons for premature study drug discontinuation will be recorded in the electronic case report form (eCRF).

4.3.2.1. Discontinuation of Study Drug

The study drug dosing will be permanently stopped if any of the following occurs:

- The subject develops TB or malignancy, excluding non-metastatic cutaneous squamous cell carcinoma or basal cell carcinoma
- Initiation of protocol-prohibited medication (Section 5.6.5)
- Subject requires treatment with CS for pericarditis during RW or LTE periods of the study
- Pregnancy or pregnancy planned during the study or within 3 months after the last study drug administration
- ALT or AST values $\geq 3 \times$ ULN associated with total bilirubin $\geq 2 \times$ ULN, with no underlying medical conditions to explain the elevated values
- Treatment with a live (attenuated) vaccine during the study
- Investigator or Sponsor's medical monitor or [REDACTED] medical monitor decides that, for safety reasons, it is in the subject's best interest
- Termination of the study by Kiniksa Pharmaceuticals

Permanent or temporary study drug discontinuation should be strongly considered at the time if any of the following occurs:

- Subject develops an opportunistic infection.
- Subject develops moderate or severe infection
- Neutrophil count $< 1.0 \times 10^3/\mu\text{L}$
- Isolated ALT or AST values $> 5 \times$ ULN
- Surgical procedure

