13.1 Appendix: ARCALYST® Prescribing Information

HIGHLIGHTS OF PRESCRIBING INFORMATION

These highlights do not include all the information needed to use ARCALYST safely and effectively. See [full prescribing information](#) for ARCALYST.

ARCALYST® (rilonacept)
Injection for Subcutaneous Use
Initial U.S. Approval: 2008

INDICATIONS AND USAGE

ARCALYST (rilonacept) is an interleukin-1 blocker indicated for the treatment of Cryopyrin-Associated Periodic Syndromes (CAPS), including Familial Cold Auto-inflammatory Syndrome (FCAS) and Muckle-Wells Syndrome (MWS) in adults and children 12 and older. (1)

DOSAGE AND ADMINISTRATION

- Adult patients 18 yrs and older: Initiate treatment with a loading dose of 320 mg delivered as two, 2-mL, subcutaneous injections of 160 mg on the same day at two different sites. Continue dosing with a once-weekly injection of 160 mg administered as a single, 2-mL, subcutaneous injection. Do not administer ARCALYST more often than once weekly. (2)
- Pediatric patients aged 12 to 17 years: Initiate treatment with a loading dose of 4.4 mg/kg, up to a maximum of 320 mg, delivered as one or two subcutaneous injections with a maximum single-injection volume of 2 mL. Continue dosing with a once-weekly injection of 2.2 mg/kg, up to a maximum of 160 mg, administered as a single subcutaneous injection, up to 2 mL. If the initial dose is given as two injections, they should be given on the same day at two different sites. Do not administer ARCALYST more often than once weekly. (2)

DOSAGE FORMS AND STRENGTHS

Sterile, single-use 20-mL, glass vial containing 220 mg of rilonacept as a lyophilized powder for reconstitution. (3)

CONTRAINDICATIONS

None. (4)

WARNINGS AND PRECAUTIONS

- Interleukin-1 blockade may interfere with immune response to infections. Serious, life-threatening infections have been reported in patients taking ARCALYST. Discontinue treatment with ARCALYST if a patient develops a serious infection. Do not initiate treatment with ARCALYST in patients with active or chronic infections. (5.1)
- Hypersensitivity reactions associated with ARCALYST administration have been rare. If a hypersensitivity reaction occurs, discontinue administration of ARCALYST and initiate appropriate therapy. (5.5)
- Live vaccines should not be given concurrently with ARCALYST. Prior to initiation of therapy with ARCALYST, patients should receive all recommended vaccinations. (5.3)

ADVERSE REACTIONS

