5 WARNINGS AND PRECAUTIONS

5.1 Infections

Interleukin-1 (IL-1) blockade may interfere with the immune response to infections. Treatment with another medication that works through inhibition of IL-1 has been associated with an increased risk of serious infections, and serious infections have been reported in patients taking ARCALYST [*see Clinical Studies (14)*]. There was a greater incidence of infections in patients on ARCALYST compared with placebo. In the controlled portion of the study, one infection was reported as severe, which was bronchitis in a patient on ARCALYST.

In an open-label extension study, one patient developed bacterial meningitis and died [*see Adverse Reactions (6.3)*]. ARCALYST should be discontinued if a patient develops a serious infection. Treatment with ARCALYST should not be initiated in patients with an active or chronic infection.

In clinical studies, ARCALYST has not been administered concomitantly with tumor necrosis factor (TNF) inhibitors. An increased incidence of serious infections has been associated with administration of

an IL-1 blocker in combination with TNF inhibitors. **Taking ARCALYST with TNF inhibitors is not recommended because this may increase the risk of serious infections.**

Drugs that affect the immune system by blocking TNF have been associated with an increased risk of reactivation of latent tuberculosis (TB). It is possible that taking drugs such as ARCALYST that block IL-1 increases the risk of TB or other atypical or opportunistic infections. Healthcare providers should follow current CDC guidelines both to evaluate for and to treat possible latent tuberculosis infections before initiating therapy with ARCALYST.

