5.5 Hypersensitivity

Hypersensitivity reactions associated with ARCALYST administration in the clinical studies were rare. If a hypersensitivity reaction occurs, administration of ARCALYST should be discontinued and appropriate therapy initiated.

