- Take ARCALYST exactly as prescribed by your healthcare provider.
- ARCALYST is given by injection under the skin (subcutaneous injection) one time each week.
- Your healthcare provider will tell and show you or your caregiver:
 - how much ARCALYST to inject
 - how to prepare your dose
 - how to give the injection
- Do not try to give ARCALYST injections until you are sure that you or your caregiver understands how to prepare and inject your dose. Call your healthcare provider or pharmacist if you have any questions about preparing and injecting your dose, or if you or your caregiver would like more training.
- If you miss a dose of ARCALYST, inject it as soon as you remember, up to the day before your next scheduled dose. The next dose should be taken at the next regularly scheduled time. If you have any questions, contact your healthcare provider.
- If you accidentally take more ARCALYST than prescribed, call your healthcare provider.

What are the possible side effects of ARCALYST?

Serious side effects may occur while you are taking and after you finish taking ARCALYST including:

- **Serious Infections.** See “**What is the most important information I should know about taking ARCALYST?**” Treatment with ARCALYST should be discontinued if you develop a serious infection.
- **Allergic Reaction.** Call your healthcare provider or seek emergency care right away if you get any of the following symptoms of an allergic reaction while taking ARCALYST:
 - rash
 - swollen face
 - trouble breathing

Common side effects with ARCALYST include:

- **Injection-site reaction.** This includes: pain, redness, swelling, itching, bruising, lumps, inflammation, skin rash, blisters, warmth, and bleeding at the injection site.
- **Upper respiratory infection.**
- **Changes in your blood cholesterol and triglycerides (lipids).** Your healthcare provider will check you for this.

These are not all the possible side effects of ARCALYST. Tell your healthcare provider about any side effects that bother you or that do not go away. For more information ask your healthcare provider or pharmacist. Call your doctor for medical advice about side effects. You may report side effects to FDA at [name].

How should I store ARCALYST?

- Keep ARCALYST in the carton it comes in.
- Store ARCALYST in a refrigerator between 36°F to 46°F (2°C to 8°C). Call your pharmacy if you have any questions.
- Always keep ARCALYST away from light.

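### The stopping rule in Section 4.3.2.1 is looser than the prescribing information for serious non-TB infection, and leaves hypersensitivity to a general safety-judgement clause

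*Protocol*

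**What the plan says.** Section 4.3.2.1 of Version 3.0 has two lists. The first gives reasons for which dosing must end permanently. Tuberculosis is the only infection in it. It also holds a general clause: dosing ends if the investigator, the sponsor's medical monitor or a second medical monitor decides, on safety grounds, that this is best for the subject.

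The second list is advisory. It opens with "Permanent or temporary study drug discontinuation should be strongly considered at the time if any of the following occurs" and includes opportunistic infection and infection of moderate or severe grade. Under Section 6.4.2.2 the severe grade includes infection for which hospitalization is indicated. Neither list names hypersensitivity.

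The prescribing information (Appendix 13.1 of Version 2.0, label revised 9/2016) is firmer:

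- Highlights: "Discontinue treatment with ARCALYST if a patient develops a serious infection".
- Label section 5.1: "ARCALYST should be discontinued if a patient develops a serious infection".
- Patient leaflet: "Treatment with ARCALYST should be discontinued if you develop a serious infection".
- Label section 5.5: "If a hypersensitivity reaction occurs, administration of ARCALYST should be discontinued and appropriate therapy initiated".

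Version 3.0 does not reprint the label. Sections 1.3.1 and 5.2 refer sites to a copy in the Pharmacy Manual.

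**The concern.** A site can hold a label that says discontinue and a protocol that says consider. After a hospitalized pneumonia, a site that weighs a stop and then continues weekly dosing has followed Section 4.3.2.1, unless a medical monitor intervenes. Another site may stop after the same event and comply equally.

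The two texts also use different triggers. The label turns on whether an infection is serious. The protocol's advisory item turns on intensity grade, which Section 6.4.2.2 defines separately from seriousness (Section 6.4.1.3). Meeting the serious adverse event criteria therefore triggers no default about the next dose.

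What is at stake is subject safety and uniform conduct across sites. One of the three serious infections that the label describes was fatal.

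**Working it through.** The plan states no figure on this point, so the main check is a comparison of texts.

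| Event | Section 4.3.2.1, Version 3.0 | Prescribing information (Version 2.0 appendix copy) |
|---|---|---|
| Tuberculosis | Permanent stop | Not compared here |
| Serious non-TB infection | Permanent or temporary stop to be weighed; mandatory only if the investigator or a monitor so decides | Discontinue |
| Hypersensitivity reaction | Not named; mandatory only if the investigator or a monitor so decides | Discontinue |

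In the second and third rows the protocol sets no default where the label does. Fixed stops are already the protocol's practice elsewhere: live vaccination and need for corticosteroids for pericarditis each end dosing without further judgement.

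**How often would it matter?**

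Inputs:
- Label section 6: 600 patients exposed, of whom 85 for at least 6 months and 65 for at least one year.
- Label section 6.3: three patients with serious infection (*Mycobacterium intracellulare*; bronchitis/sinusitis; fatal pneumococcal meningitis).
- Protocol Section 7.4: about 56 subjects planned, no more than 100 anticipated.

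Rate: 3/600 = 0.5%; exact (Clopper-Pearson) 95% CI 0.10% to 1.45%.

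| | 56 subjects | 100 subjects |
|---|---|---|
| Expected cases, n × 0.005 | 0.28 | 0.50 |
| Range over the CI | 0.06 to 0.81 | 0.10 to 1.45 |
| P(at least one) = 1 − 0.995^n | 24.5% | 39.4% |
| P(at most two), binomial | 99.7% | 98.6% |

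The rate may be too low for longer dosing, because 600 − 85 = 515 of those patients are not stated to have reached 6 months. For the same reason no usable rate per patient-year can be formed. Counting those 515 as zero gives 65 × 1 + 20 × 0.5 = 75 patient-years and 3/75 = 0.04 per patient-year, which is only a ceiling.

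For hypersensitivity the documents give no count. Section 1.3.1 and the label call it rare.

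**The case against.** The strongest reply is that the discretion is deliberate. The Amendment 1 summary of changes removed an automatic stop for any serious or intolerable adverse event and gave two reasons. One was to spare hospitalization for pericarditis and other events that would not otherwise call for stopping. The other was that intolerable events are already handled by the safety-judgement clause. That clause sits in the permanent-stop list, and any of three decision-makers can invoke it. Serious events must also be reported within 24 hours (Section 6.4.6), and the DMC reviews safety data (Section 6.7.1).

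Much of this stands. The clause is a natural home for a systemic hypersensitivity reaction, so that half of the point asks for explicit wording more than it exposes an uncovered event. For serious infection the reply is weaker. The clause acts only once someone decides, and reporting and DMC review set no default for the next dose. The first amendment reason does not describe an event for which the label says discontinue.

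It is also fair that the label copy in hand belongs to Version 2.0. If the Pharmacy Manual copy differs, the mismatch is unproven.

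Three stronger readings are tempting and should not be drawn:

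- **Version 3.0 contradicts its own exclusions.** Criteria 16 ("Has a known or suspected current active infection"), 17 ("Has had a serious infection, has been admitted to the hospital for an infection") and 21 ("Has a known hypersensitivity to ARCALYST") bar entry. Entry criteria need no stopping counterpart: the hemoglobin limit in criterion 19 has none and none is expected.
- **Home dosing enlarges the risk.** Most weekly doses are given outside the clinic (Section 5.2.3), but those in the randomized period include placebo, and where a dose is given does not decide whether the stopping rule is adequate.
- **The result is biased.** Nothing here bears on the randomized comparison; the primary analysis follows assigned treatment (Section 7.5).

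**Conclusion.** The point holds as a cheap safety improvement. For serious non-TB infection, Version 3.0 states a rule looser than the prescribing information. For systemic hypersensitivity it relies on a general clause where the label gives a specific instruction. The protocol does not forbid stopping in either case.

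The size is small: about 0.3 to 0.5 serious infections expected, and a 24% to 39% chance of at least one. This assumes that the three label cases are among the 600 patients, that the rate carries over to recurrent pericarditis, and that the Pharmacy Manual label matches the Version 2.0 copy. The 0.5% is not a programme-wide rate: Section 1.3.1 reports 2243 exposed subjects but no infection count. No size can be given for hypersensitivity.

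**What to change.** In Section 4.3.2.1:

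1. Require study drug to be stopped for any infection meeting the serious adverse event criteria of Section 6.4.1.3. Allow restart only after resolution and with medical monitor agreement, and say openly that this relaxes the label, which mentions no restart.
2. Add systemic hypersensitivity reaction to the permanent-stop list.
3. Leave the advisory items for opportunistic infection and for moderate or severe infection as they are for all non-serious cases, so that a severe infection that is not serious stays covered. Leave tuberculosis as it is.

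Hospitalization for pericarditis stays outside the rule, so the purpose of Amendment 1 is kept.

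The text is a line or two, but it is a protocol amendment needing IRB/IEC submission and, where required, regulatory submission (Section 11.2.1). At 0.5%, probably 0 to 2 extra infection stops would follow. In the randomized period the rule is applied blind, so it would also stop placebo subjects. A subject stopped permanently loses the option of up to 24 months of open-label rilonacept, because Section 3.1.4 opens the extension to those who did not discontinue study drug. The restart provision limits that loss for infection; for hypersensitivity it remains.
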